From 2021 to present, SCC has been pilot tested at the U.S. Air Force Academy (USAFA) among basic cadets (referred to as basics/basic cadets until they complete Basic Cadet Training [BCT]). Specifically, in summer 2021, the program was pilot tested with nearly 160 basics (i.e., 1 BCT squadron). Based on 2021 pilot study findings and feedback obtained from basics, instructors, and website metadata, changes were made to the SCC program, ranging from minor (slight changes to the assessment instruments and timing of program components) to substantive (e.g., moving the tailored programming from a tablet to the web). This revised, web-based version of SCC was then evaluated in the entire 2022 BCT class, wherein half of the class was assigned to receive SCC and the other half of the class was assigned to receive standard SAPR Cadet Healthy Personal Skills (CHiPS) training, which is the USAFA BCT "Training-as-Usual" (TAU) program. SCC was delivered by USAFA HRPP-approved SAPR and affiliated staff/volunteers; CHiPS was delivered by contracted CHiPS instructors. Anonymous web-based surveys were administered at pre-test and post-test during BCT, 3-month follow-up, and 9-month follow-up. Analyses of 2022-2023 APY cohort data are ongoing, but initial findings suggest that SCC was acceptable, feasible, and effective on immediate (i.e., pre-test to post-test) outcomes. Low (<20%) DSAT response rates have also highlighted difficulties with follow-up assessment retention.

One interesting finding from the 2022 pilot study was that SCC yielded improvements on certain alcohol-related outcomes. This is of importance because (a) alcohol use is a risk factor for sexual assault, (b) alcohol

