misuse is associated with other negative effects on health and well-being, and (c) the Department of Defense is interested in cross-cutting prevention efforts that protect against multiple adverse outcomes such as alcohol misuse and sexual assault. As SCC is a sexual assault prevention program and accordingly addresses alcohol use to the extent that alcohol is related to sexual assault risk or experiences, there is benefit in determining whether additional alcohol misuse prevention content is associated with even stronger desirable effects on alcohol use-related outcomes. One candidate alcohol misuse prevention program is eCHECKUP TO GO, a brief (30-minute), personalized, web-based alcohol misuse prevention program developed by San Diego State University (SDSU). Based on an eCHECKUP TO GO program user's anonymous alcohol-related demographic information (e.g., biological factors influencing BAC) and experiences (e.g., alcohol use behavior prior to arriving at USAFA), personalized feedback is presented to modify cognitive risk factors for alcohol use and correct inaccurate norms perceptions that may increase risk for alcohol (mis)use. eCHECKUP TO GO has demonstrated feasibility, acceptability, and efficacy in previous studies of first-year undergraduate students (Doumas & Anderson, 2009; Doumas, Kane, Navarro, & Roman, 2011; Henry, Lange & Wilson, 2004; Hustad, Barnett, Borsari, & Jackson, in 2010; Lane & Schmidt, 2007; Steiner, Woodall & Yeagley, 2005; Wilson, Henry & Lange, 2005). In a different USAFA study (FAC20220024H HS-2022-0009), eCHECKUP TO GO was successfully beta-tested in a small sample of 22 volunteer cadets; findings suggested eCHECKUP could be acceptable and feasible to implement at USAFA. Taken together, there is merit to conducting a follow-up pilot study to investigate whether incorporating eCHECKUP TO GO yields additional prevention programming benefits above and beyond SCC or CHiPS alone.

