We hypothesize that there will be some variability in program acceptability among cadets in the five different SCC training programs (healthy relationships/bystander intervention promotion; male revictimization prevention; male primary victimization prevention; female revictimization prevention; female primary victimization prevention). Based on our prior work at BMT and the 2021 USAFA BCT pilot study, we expect data will support SCC implementation feasibility and acceptability as indicated by few technological issues and high implementation fidelity among instructors. We also expect to observe meaningful increases from pre-test to post-test in knowledge of sexual assault and consent (across all participants), self-efficacy to resist unwanted sexual advances (among those who receive the primary victimization and revictimization prevention trainings), and bystander intentions (among those who receive the healthy relationships and perpetration prevention training). Based on 2022-2023 pilot study findings and the supporting theoretical and empirical evidence, we also expect all basics to show meaningful improvements in alcohol-related outcomes from pre- to post-training, but even stronger improvements among basics who receive eCHECKUP TO GO compared to basics who do not also complete eCHECKUP TO GO. This study will build on our prior work at BMT and the USAFA BCT pilot studies by examining whether anticipated effects are sustained over a 3- and 9-month follow-up period, which will help inform ideal timing of implementation and/or the need for booster training sometime following BCT. Follow-up assessments at 3 and 9 months will also allow for the assessment of changes in low-base-rate or occasional behaviors that may require more time to be observed.

Objective 1: Assess the feasibility and acceptability of implementing SCC with four-degree USAFA basic cadets in BCT (referred to as basics/basic cadets until they complete BCT).

Objective 2: Assess SCC program efficacy on proximal (knowledge, attitudes, beliefs, self-efficacy) and distal (protective behavior use, first-year sexual assault prevalence) outcomes compared to the Cadet Healthy Interpersonal Skills (CHiPS) TAU program across cadets' first year at USAFA.

Objective 3: Compare the efficacy of SCC alone to the combination of SCC plus eCHECKUP TO GO for alcohol use outcomes.

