Data from the 2022-2023 and 2023-2024 APY studies will be merged to maximize statistical power and our ability to assess and differentiate program effects as described in Objectives 1-3, above.

7. Study Methods and Procedures

[figure not shown]
Describe the study methodology. Describe in detail all procedures the subjects will do in the order that they will do them, or what will be done to the subjects, (i.e., tasks and information to be gathered from or about the participants). Indicate whether subjects will be randomized for the study and describe the control and

experimental groups. Include descriptions of the facilities, equipment, and safety precautions, if applicable, the time for each task and total time for participation. Attach the data collection instruments or data items (e.g. interview script, survey tool, data collection form for existing data). Describe the analysis you will conduct to achieve your objectives. Your description of the research procedures should focus only on those procedures associated with participating in the research. If a participant will complete a given procedure regardless of whether or not s/he consents to participate in the research, then this procedure is not part of the research design.

Methods

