Endorsement by the Department Head or an individual with similar responsibility and authority. (Note: No individual listed on this protocol may sign this section.)

I approve this research to be conducted by personnel within my department. I will ensure that the research personnel in my department comply with all IRB laws, regulations, policies, decisions, conditions, and requirements.

[name], Colonel, USAF

Vice Superintendent

US Air Force Academy

(Signature waived for revision submission)

STATISTICAL ANALYSIS PLAN

Analysis Plan

Because of low follow-up survey participation rates among cadets who provided pretest survey data at the 3-month (13%) and 9-month (5%) assessments, only analyses of pre- to posttest data were conducted.¹ The outcomes examined and reported in this study were selected both because they were assessed at pre- and posttest and because they represent alcohol- and sexual assault-related factors that could reasonably change after participation in an integrated alcohol misuse and sexual assault prevention training (i.e., attitudes and knowledge). Study procedures and materials were reviewed by the USAFA Institutional Review Board and U.S. Army Medical Research and Development Command's Office of Human Research Oversight.

Descriptive statistics were computed for all variables to examine completeness and distribution. Group comparison tests (t-tests, chi-square tests, one-way analysis of variance) of participant characteristics at pretest were conducted to identify differences between conditions. To assess differences in change from pre- to posttest in outcomes by condition, we conducted mixed-effects multilevel models separately for each continuous outcome variable, with SCC + eCHECKUP TO GO set as the referent group. Independent variables included study condition (4-level: TAU, TAU + eCHECKUP TO GO, SCC, SCC+eCHECKUP TO GO), time, and time*condition. Covariates included cohort, race/ethnicity, and peer victimization. To examine moderation by sex, the models were replicated with the addition of interaction terms sex*time, condition*sex, and time*condition*sex. If the three-way interaction term was significant, models stratified by sex were computed. The same procedures were followed to determine whether condition effects were moderated by prior alcohol use. All analyses were computed in SAS version 9.4.

Measures: Sample Characteristics at Pretest

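### A merged SCC versus CHiPS result on alcohol outcomes would not be independent confirmation, because the 2022 records that helped to suggest the expectation are part of the test and no 2023-only result is fixed

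*Combined protocol and SAP*

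**What the plan says.** Protocol section 5 (Background) states that analysis of the 2022 cohort was still under way but that "initial findings suggest that SCC was acceptable, feasible, and effective on immediate (i.e., pre-test to post-test) outcomes". It adds: "One interesting finding from the 2022 pilot study was that SCC yielded improvements on certain alcohol-related outcomes". That observation leads into the case for adding an alcohol programme in 2023.

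Section 6 (Objectives) opens the alcohol hypothesis with: "Based on 2022-2023 pilot study findings and the supporting theoretical and empirical evidence, we also expect all basics to show meaningful improvements". The same sentence then expects "even stronger improvements among basics who receive eCHECKUP TO GO compared to basics who do not also complete eCHECKUP TO GO". The only objective that names alcohol is this one: "Objective 3: Compare the efficacy of SCC alone to the combination of SCC plus eCHECKUP TO GO for alcohol use outcomes". Objective 2 compares SCC with CHiPS on proximal outcomes, and the Data Analysis Plan in section 7 counts alcohol beliefs and readiness to change among these.

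Section 6 closes with "Data from the 2022-2023 and 2023-2024 APY studies will be merged to maximize statistical power", and applies this to all three objectives. The Data Analysis Plan repeats the merging where possible and appropriate. It allows that cohort-specific analyses might be wanted in some cases, without naming any.

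The SAP (Analysis Plan) fits a four-level condition, time and their interaction, with SCC + eCHECKUP TO GO as the reference. On cohort it says only: "Covariates included cohort, race/ethnicity, and peer victimization". Its two alcohol outcomes are normative perceptions of peer drinking and readiness to change.

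**The concern.** When a result is noticed in one data set, and that data set is then pooled with new data to test it, the chance part of the first result is carried into the test. A cohort covariate does not remove it. It absorbs a difference in level between years, whereas the chance part here would be a difference between arms in pre-to-post change within 2022. A reader of the merged analysis could take a favourable SCC versus CHiPS result on alcohol as a second, independent finding when part of it is the first one.

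At stake are the false-positive rate and the effect size for SCC on alcohol outcomes. The same chance gain would also enter the comparison of SCC + eCHECKUP with SCC, but in the opposite direction, because the 2022 SCC squadrons belong only to the comparator.

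**Working it through.** **Inputs.** The 2023 class has 8 squadrons, 4 for SCC and 4 for CHiPS (section 5). Three of each four also receive eCHECKUP (section 7), so the 2023 cells are SCC 1, SCC + eCHECKUP 3, CHiPS 1, CHiPS + eCHECKUP 3. In 2022 there were only SCC and CHiPS, half the class each (sections 5 and 7). No squadron count is given for 2022, so I assume 4 and 4. No alpha is stated; I assume 0.05 two-sided, which is 0.025 in the favourable direction. Section 8 gives no sample size or power, so there is no planned figure to reproduce. I also assume squadrons of equal size and variance and a known-variance z test.

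**1. SCC versus CHiPS, merged.** Let z1 be the 2022 statistic, z2 the 2023 statistic, and f the share of the information that comes from 2022. Then

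z(merged) = √f·z1 + √(1−f)·z2,

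and the correlation of z(merged) with z1 is √f. With no true effect, P(z(merged) > 1.96 given z1 > c), from the bivariate normal distribution, is:

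| How 2022 was picked out | f = 0.5 | Other f |
|---|---|---|
| Not picked out; merged test run regardless | 0.025 | 0.025 |
| Right direction only (c = 0) | 0.049 | – |
| c = 1.28 | 0.172 | – |
| Significant (c = 1.96) | 0.338 | 0.273 at f = 0.4; 0.408 at f = 0.6 |

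**2. The share f under the SAP's coding.** Pooled over eCHECKUP, each year has 4 v 4 squadrons, so f = 0.5. For SCC-only versus CHiPS-only the squadrons are 4 v 4 in 2022 and 1 v 1 in 2023, so f = 4/(4 + 1) = 0.8, and the last row of the table becomes 0.58.

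**3. Picking the best of several outcomes.** If the best of K independent alcohol outcomes in 2022 is carried forward, with no significance required, simulation gives a merged one-direction error of 0.046, 0.063 and 0.093 for K = 2, 3 and 5 at f = 0.5. Testing the same outcome on 2023 alone gives 0.025.

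**4. Objective 3 (SCC + eCHECKUP minus SCC).** Work in squadron SD units, and suppose 2022 reached z1 > 1.96 by chance.
- E[z1 given z1 > 1.96] = φ(1.96)/0.025 = 2.34.
- The expected 2022 SCC mean is (0.25/√0.5) × 2.34 = 0.83.
- The merged SCC-only mean uses 5 squadrons, 4 of them from 2022, so its expected shift is 0.8 × 0.83 = 0.66.
- The SE of the contrast is √(1/3 + 1/5) = 0.73.
- The mean z is −0.66/0.73 ≈ −0.90.

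A simulation of 1,000,000 null trials, of which 25,236 met the condition, agrees: mean z −0.90, falsely significant in favour 0.001, falsely significant against 0.128. Adding a cohort-by-time term reduces the mean z to −0.68 but does not remove it. The same mechanism works in favour of the eCHECKUP contrasts with CHiPS alone: mean z about +0.9 and a false-positive rate of about 0.13.

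**5. Precision of 2023 alone (SE, squadron SD = 1).**
- Pooled 4 v 4: √(1/4 + 1/4) = 0.71, against √(1/8 + 1/8) = 0.50 for 8 v 8 merged; ratio 1.4.
- SCC effect averaged over eCHECKUP levels: ½√(1 + 1 + 1/3 + 1/3) = 0.82, against ½√(1/5 + 1/5 + 1/3 + 1/3) = 0.52; ratio 1.6.
- SCC-only versus CHiPS-only: √2 = 1.41, against √(2/5) = 0.63; ratio 2.2.
- SCC + eCHECKUP versus SCC: √(1/3 + 1) = 1.15, against 0.73; ratio 1.6.

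**The case against.** Several points on the other side are sound.

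- **Objective 3 did not come from 2022.** A reader might infer that the whole alcohol hypothesis, including the added eCHECKUP effect, was suggested by 2022 and would be confirmed by it. The documents do not support that. There was no eCHECKUP arm in 2022, and section 5 rests that effect on outside work: "eCHECKUP TO GO has demonstrated feasibility, acceptability, and efficacy in previous studies of first-year undergraduate students". Step 4 shows that a chance 2022 SCC gain would count against Objective 3.
- **No superiority claim is stated.** Section 6 expects all basics to improve, more so with eCHECKUP. It does not say that SCC will beat CHiPS on alcohol, and it cites theory and other evidence besides 2022. Objective 2 still makes the SCC versus CHiPS comparison on proximal outcomes, so the result would be produced and read.
- **The selection is not documented.** Nothing says which alcohol outcomes improved in 2022, against what comparator, or whether any reached significance. The SAP gives a different reason for its choice of outcomes: they were measured at both times and could plausibly change. The 34% and 58% are therefore not the Type I error rate of the plan; they are what would follow from a condition that the documents do not report.
- **SCC versus CHiPS is not a direct coefficient.** With SCC + eCHECKUP as reference it has to be formed as a contrast. That makes it less prominent but does not change its content.
- **This is pilot work, and cohort-specific analysis is allowed.** Both are true, and both weaken any claim to confirmation. Neither fixes a 2023-only result for alcohol.

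**Conclusion.** The point holds for SCC versus CHiPS on alcohol outcomes. The expectation was drawn partly from 2022 results already seen, those records are in the merged test, and nothing in the SAP separates them. A merged result is not independent confirmation.

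The size is uncertain because the route from the 2022 results to the hypothesis is not reported. The plausible range runs from no inflation (2.5%), through 4.9%, to 34%, or 58% for the squadrons without eCHECKUP. These figures rest on a 0.05 two-sided level and on 4 v 4 equal squadrons in 2022. The direction of the bias under selection does not depend on either.

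For SCC + eCHECKUP versus SCC the concern is the reverse: a chance 2022 gain would tend to hide a benefit. This is a matter of labelling and reporting. It is not a reason to abandon the merged analysis.

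**What to change.** In the SAP, for normative perceptions and readiness to change:

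1. Report the SCC–CHiPS difference in pre-to-post change for 2022, for 2023 and merged, side by side. Name the 2023 estimate pooled over eCHECKUP levels (4 v 4 squadrons) as the independent replication. The SAP does not currently define this contrast. The 3-to-1 eCHECKUP split is the same in both arms, so the comparison is balanced, but it estimates the SCC effect in a mix that differs from 2022, and the text should say so.
2. Show SCC + eCHECKUP versus SCC within 2023 beside the merged estimate.
3. Label the 2022 and merged SCC–CHiPS alcohol results as exploratory.
4. State which alcohol outcomes improved in 2022 and by what criterion, so that a reader can place the result in the range above.

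The cost is some wording and a few more output columns; no new data are needed, and it can still be done although the SAP is written in the past tense. The 2023-only estimates are less precise, with SEs about 1.4, 1.6 or 2.2 times the merged ones for the SCC–CHiPS contrasts in step 5. That is why the merged analysis should stay beside them.

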The baseline survey includes the screener instrument and the pre-test outcome measures (Attachments 7a and 7b, respectively). The baseline survey will be administered to the entire incoming class during the SAPR/CWIC BCT briefing, which occurs prior to the designated SAPR training time during which SCC, eCHECKUP TO GO (for the 2023-2024 cohort), and CHiPS will be delivered. The screener will assess demographic characteristics, prior sexual assault experiences, and other forms of trauma that have been empirically linked to increased risk for sexual assault. Upon receiving a study ID, basics will complete a screening instrument, which will determine their classification within one of five prevention categories: female primary victimization or revictimization prevention; male primary victimization or revictimization prevention; or healthy relationships & bystander intervention promotion. For basics assigned to receive SCC, the screener survey will also route the basic into the corresponding tailored web-based SCC programming. Immediately following the screener, cadets will complete the pre-test assessment, which assesses knowledge, attitudes, and behavioral intentions specific to their assigned program (skip patterns will be utilized to tailor measures to each participant's program assignment based on the screening items and to minimize respondent burden).

At the end of each of the 3 designated training sessions, basics assigned to receive SCC will be asked to complete a brief (less than 5 minutes) acceptability survey. Basics assigned to receive CHiPS will complete a similar acceptability survey after Day 3 only. (See Attachment 8 for copies of both acceptability instruments). After completing the Day 3 acceptability survey, all basics will complete the post-test survey to examine any immediate program-related changes in knowledge, attitudes, and behavioral intentions (Attachment 7c). All acceptability and post-test survey instruments are integrated into the overall 6-6.5-hour training time. All assessments are derived from validated, gold-standard measures published in the sexual assault and alcohol misuse prevention empirical literature. As stated earlier, the Measurement x Timepoint Table (Attachment 9) summarizes which constructs will be assessed during each timepoint throughout the study.

Follow-up Assessments

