measures, as they account for nested data (multiple assessments within person), which violate the assumption of independence associated with traditional regression methods. Further, latent growth models allow for modeling of non-linear trends, which are common when evaluating program effects, as initial improvements often plateau or drop back down over time. To the extent that we are powered to do so (likely only for male healthy relationships and female primary victimization programs), mediation models will test program effects on hypothesized mechanisms of change. For example, we hypothesize, based on prior work, that men exposed to the healthy relationships and bystander intervention program will exhibit increased intentions to intervene, which will in turn increase actual bystander intervention behavior.

Results will be analyzed both at the aggregate level and by program intervention group. Specifically, we will closely monitor screener data to ensure the automated screening algorithm functions properly and that cadets are receiving the content that is most appropriate. We will also compare rates of prior victimization and perpetration recorded via comprehensive assessment versus a brief assessment to determine whether a brief assessment could be sufficient for group assignment while also minimizing cadet burden. We will examine trends in responses across groups (e.g., higher levels of enjoyment or engagement among cadets in one training group over another) and visually examine trends in knowledge and attitude change to ensure effects are in the intended direction. This will also allow us to monitor for unexpected trends, including potential negative impacts on cadets.

8. Sample Size and Power Analysis

(Applies to “Full IRB Review” submissions) Describe how many participants you will need in total and for each subgroup in the study. Explain why your sample sizes are sufficient to achieve your study objectives. If appropriate, provide the details of a statistical power analysis including the assumptions underlying the analysis that helped you to arrive at your chosen sample size. Note: For minimal risk studies, the IRB asks for the minimum number of subjects that you require. You may exceed this minimum without amending your study. For greater than minimal risk studies, the IRB approves a maximum number of subjects. You may not exceed this number without an amendment approved by the IRB.

N/A, Exempt status

9. Subject Recruitment Methods

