Sociodemographic information. All participants self-reported their age, sex, race/ethnicity, and sexual orientation.

Peer victimization. Past-12-month peer victimization was assessed with a three-item measure adapted from the Military Workplace Violence Study (Hourani et al., 2018). Participants self-reported how often one or more peers threatened their physical safety, put them through hazing activities, or harassed or bullied them (1: None of the time; 5: All of the time). Items were summed to create a continuous score.

Prior alcohol use. Participants self-reported their past-30-day alcohol use (as the number of drinks they typically had each day during a typical week during the month before arriving at USAFA) and were dichotomized based on whether they reported no alcohol use or any use.

Prior sexual assault victimization. Participants completed a 20-item measure derived from the Sexual Experiences Survey–Victimization (Testa et al., 2010) adapted based on cognitive testing with airmen (Goldstein & Scaglione et al., 2024). Items assessed whether participants had ever experienced unwanted sexual touching, intercourse, oral sex, anal sex, or other penetration. Participants were dichotomized based on whether they reported any or no prior sexual assault victimization.

¹ Analyses comparing 3- and 9-month survey responders and nonresponders identified systematic differences (in sex, prior alcohol use at pretest, and pretest readiness to change alcohol use behaviors) between the subsample of responders and total sample, indicating that presenting follow-up data could misrepresent the true program effects overall.

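### Comparing rates from the brief and comprehensive assessments cannot show that the brief one assigns the same cadets to the same programme; a within-cadet cross-classification would

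*Combined protocol and SAP*

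**What the plan says.** In protocol section 7, Data Analysis Plan, the team undertakes to "compare rates of prior victimization and perpetration recorded via comprehensive assessment versus a brief assessment to determine whether a brief assessment could be sufficient" for assigning cadets to groups, with the further aim of reducing the burden on cadets. So both the metric (rates) and the question (group assignment) are stated. No person-level agreement measure, tolerance or acceptance rule is given.

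Two neighbouring statements bear on this. The paragraph opens with "Results will be analyzed both at the aggregate level and by program intervention group", and the team will also "closely monitor screener data to ensure the automated screening algorithm functions properly". Neither is described as a check of the brief result against the comprehensive one.

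The BCT Assessments part of section 7 shows what the screener result is used for: "basics will complete a screening instrument, which will determine their classification within one of five prevention categories". For cadets allocated to SCC, "the screener survey will also route the basic into the corresponding tailored web-based SCC programming". The Background (section 5) likewise describes electronic routing to one of five tailored programmes after screening for gender and individual risk factors.

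The SAP does not mention the brief-versus-comprehensive comparison. Its section on sample characteristics at pretest describes a 20-item victimization measure ("Participants were dichotomized based on whether they reported any or no prior sexual assault victimization") and a 5-item perpetration measure, also split into any or none. It does not say whether either is the comprehensive or the brief version.

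**The concern.** The metric does not answer the question. Whether a brief form is good enough for assignment depends on whether it puts each cadet in the category that the comprehensive form would. A rate is a marginal total. It says how many cadets screen positive on each form, not whether they are the same cadets. Missed cases lower the brief rate, false positives raise it, and the two can cancel. Where the rates do differ, the difference still does not say how many cadets would change category.

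At stake is the soundness of any later statement that the brief form suffices. Tailoring by prior experience is central to SCC, and the Background singles out cadets victimized before arrival as a smaller, higher-risk subgroup. A brief form with a similar rate but poor individual agreement could place some of them in primary-prevention content, and some cadets without that history in revictimization content.

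**Working it through.** **Is there a figure to reproduce?** No. The documents give no prevalence, accuracy, sample size or agreement target for this comparison. The values of p and s below are assumptions.

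**Set-up.** Take the comprehensive result as the reference for one any-or-none item. Let p be its rate, s the sensitivity of the brief form and c its specificity.

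- Missed positives, as a share of all cadets: p(1 − s)
- False positives, as a share of all cadets: (1 − p)(1 − c)
- Rate on the brief form: ps + (1 − p)(1 − c)

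The two rates are equal when (1 − p)(1 − c) = p(1 − s), that is, c = 1 − p(1 − s)/(1 − p). The share misclassified is then 2p(1 − s).

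**Worked case: p = 20%, s = 60%.**

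- Missed: 0.20 × 0.40 = 8%
- Specificity for equal rates: 1 − 0.08/0.80 = 90%
- False positives: 0.80 × 0.10 = 8%
- Brief rate: 0.12 + 0.08 = 20%, against 20% on the comprehensive form
- Misclassified on the item: 8% + 8% = 16%

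Per 1000 cadets, 80 of 200 positives are missed and 80 of 800 negatives are flagged, with a difference in rates of zero.

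**Range.** Share of cadets misclassified on the item when the two rates are identical:

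| Assumed p | s = 90% | s = 70% | s = 50% |
|---|---|---|---|
| 5% | 1% | 3% | 5% |
| 10% | 2% | 6% | 10% |
| 20% | 4% | 12% | 20% |
| 30% | 6% | 18% | 30% |

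**If the brief form only under-detects (c = 100%).** The brief rate is ps, so the rates separate. At p = 20%, s = 60% they are 12% and 20%, which the planned comparison would reveal. At p = 10%, s = 80% they are 8% and 10%. That gap of 2 percentage points could be read as small, although one positive in five is missed, and the plan gives no tolerance for judging it.

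**What cannot be computed.** Routing uses gender and several risk factors across five categories, and the algorithm is not in the text. An error on one item need not change a cadet's category, so none of these percentages is a misrouting rate.

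**The case against.** The strongest reply is that the sentence is under-specified rather than wrong. It says rates, not overall rates, and the paragraph promises results by programme group as well as in aggregate. Brief-form rates tabulated within groups defined by the comprehensive result would be the sensitivity and 1 − specificity. This stands as a possibility, but the plan does not say that the comparison will be made this way or which assessment forms the groups. The monitoring of screener data is a genuine commitment too, but it has no metric and is not tied to the brief form.

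A second reply is that exact cancellation is a selected scenario. That is fair. If, for example, the brief items were a subset of the comprehensive ones, false positives would be ruled out and the rates would diverge. The screener is listed as Attachment 7a but is not in the text, so how likely cancellation is cannot be judged.

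A third is that this is an exploratory side-check. That also stands: it is not among Objectives 1 to 3, and the wording asks only whether the brief form could be sufficient.

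A reader might go further and infer that the comparison will settle how later classes are screened. The documents do not say so. They state only that the Academy may choose to continue the programme, and they set no rule for adopting a brief form.

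**Conclusion.** The point holds in a limited form. The plan names a comparison of rates for a question about individual assignment, and rates cannot answer that question. This rests on algebra and on the protocol's own account of cadet-by-cadet classification.

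Its practical size is unknown. The 16% in the worked case, and the 1% to 30% across the table, are hypothetical item-level errors that assume the prevalence, the sensitivity and exact cancellation. They should not be read as the share of cadets sent to the wrong programme, which the documents do not allow anyone to derive. Nor does the point reach the trial's efficacy results: the comparison does not enter the SAP's pre- to posttest models. It is a cheap improvement to a secondary aim.

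**What to change.** In the Data Analysis Plan, replace or supplement the rate comparison with the following, where the same cadets answered both versions:

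- a within-cadet cross-classification of the brief against the comprehensive result, separately for victimization and perpetration;
- the sensitivity and specificity of the brief form relative to the comprehensive one, each with a 95% CI;
- the percentage of cadets whose programme category would change, with a 95% CI, obtained by running the assignment rule on each version.

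Base any statement that the brief assessment is sufficient on these figures, not on similar rates.

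The documents do not say whether the same cadets answered both versions, so the plan should state this. If they did not, report the two rates descriptively and draw no conclusion about sufficiency for group assignment.

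The cost is a few lines of text and one extra cross-tabulation for each of the two measures, with no new data if both versions were given to the same cadets. The downside is that the brief form may look less favourable than it does on rates alone.
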